## Statistical Analysis Plan

In addition, patients with TAS-120 dose reductions from the previous cycle, patients with dose reductions due to AEs, patients with dose held/delays due to AEs, and patients with treatment discontinuations due to AEs will be summarized for the entire study.

All recorded information for study medication administration and accountability for TAS-120 will be listed.

### 10.2. DOSE LIMITING TOXICITY

The dose limiting toxicity in the first cycle of Phase 1 Dose Escalation will be presented by dose level and overall for Safety Population by dosing schedule. The compliance to the 3+3 design scheme for dose escalation rules will be shown in the table.

#### 10.3. ADVERSE EVENTS

An adverse event (AE) is any untoward medical condition that occurs in a patient while participating in this clinical study. Adverse events will be coded according to the Medical Dictionary for Regulatory Activities (MedDRA) terminology and the severity of the toxicities will be graded according to the NCI CTCAE, v4.03, where applicable.

Treatment-Emergent Adverse Events (TEAEs) are those adverse events that occur from the initiation of TAS-120 medication administration to 30 days after the last dose of study medication, and do not necessarily have a causal relationship to the use of the study medication. Treatment-Emergent Adverse Events (simply referred to as adverse events in summary tables) will be summarized.

A Serious Adverse Event (SAE) is an AE which falls into one or more of the following categories:

- a. Results in death
- b. Is life-threatening
- c. Requires inpatient hospitalization or prolongation of existing hospitalization
- d. Results in persistent or significant disability or incapacity
- e. Is a congenital anomaly/birth defect
- f. Is any other important medical event

All deaths occurring through the 30-day follow-up period is reported as outcomes of SAEs. Signs, symptoms and complications related to disease progression should be reported as AE or SAEs. Clinical disease progression may only be reported as an SAE term if none of the relevant signs or symptoms supports a fatal outcome. While those

 $\mathsf{CC}$ 

Sponsor: Taiho Oncology, Inc. Protocol: TPU-TAS-120-101

Version: 3.3, Phase 1 Dose Escalation Only

## Statistical Analysis Plan

severe AEs are classified into Grade 3 AEs, those life-threatening AEs are classified into Grade 4 AEs.

Adverse Events will be summarized by dose level and overall for Phase 1 Dose Escalation. AEs will be presented by system organ class in the overall column in decreasing order. Within each system organ class, the AEs will be displayed by preferred term (PT) in decreasing order in the overall column.

The following adverse event summary tables will be generated:

- 1) An overall summary with the number and percentage of patients reporting AEs, serious AEs, grade 3 or higher AEs, treatment-related AEs, Dose Limiting Toxicities, AEs leading to study treatment (TAS-120) discontinuation and AEs with outcome of deaths. Summary with combined groups will also be generated.
- 2) AEs overall and by system organ class and preferred term.
  - In the summary, a patient is counted once at the system organ class and once at each preferred term within the system organ class. Additional summary by system organ class, preferred term and grade (including Total and >= grade 3 categories) will also be generated.
- 3) Study-treatment-related AEs overall and by system organ class and preferred term. Additional summary by system organ class, preferred term and grade (including Total and >= grade 3 categories) will also be generated.
  - All those AEs with relationship to TAS-120 marked as "Related" or missing will be reported in the table.
- 4) AEs by highest grade (worse severity) overall and by system organ class and preferred term.
  - In the summary, a patient is counted once at the highest grade for which the event occurred in the system organ class and the highest grade for each unique preferred term within that system organ class. Therefore, patients may only contribute once to each preferred term and once to each system organ class. The missing severity grade will be reported in a separate category.
- 5) Serious AEs, overall and by system organ class and preferred term. Additional summary by system organ class, preferred term and grade (including Total and >= grade 3 categories) will also be generated.
- 6) Grade 3 or higher AEs, overall and by system organ class and preferred term

Sponsor: Taiho Oncology, Inc. Protocol: TPU-TAS-120-101

Version: 3.3, Phase 1 Dose Escalation Only

## Statistical Analysis Plan

- 7) Study-treatment related AEs by grade (severity), overall and by system organ class and preferred term
- 8) AEs leading to study treatment termination, overall and by system organ class and preferred term. Additional summary by system organ class, preferred term and grade (including Total and >= grade 3 categories) will also be generated.
- 9) AEs with outcome of deaths, overall and by system organ class and preferred term

In addition, the time to onset of some special AEs of interest in the study may be summarized if appropriate.

Dose limiting toxicity list will be provided based on the DLT evaluable population.

### 10.4. LABORATORY EVALUATIONS

Blood samples for hematology, coagulation and serum chemistry assessments are collected and measured at baseline (within 7 days prior to study medication administration on Day 1 of Cycle 1), within 24 hours prior to Day 1 study drug administration of each cycle, anytime on Day 8 and Day 15 of Cycle 1 and Cycle 2, the end of treatment visit and 30-day safety follow-up visit. Starting with Cycle 3, the Day 8 assessment is not required, unless deemed clinically indicated by the investigator. Creatine kinase needs to be repeated on Day 1 of Cycle 2. Fractionation of CK into its isoforms must be performed in case of an elevation of CK (unless the isoform CK [isoform skeletal and heart muscle] [CK-MM and CK-MB] was tested, in which case a fractionation is no longer needed). If CK is abnormally elevated at Screening (Day -7 to -1), the results of the fractionation must be available prior to starting TAS-120 treatment for that patient.

Hematology and coagulation parameters that will be measured include: RBC count, Hemoglobin, Hematocrit, Platelets, INR, APTT, White blood cell (WBC) count with differential, Neutrophils, Lymphocytes, Monocytes, Eosinophils, Basophils. Serum chemistry parameters that will be measured include: ALT (SGPT), AST (SGOT), Alkaline phosphatase, Total bilirubin, Albumin, Creatinine, Blood urea nitrogen (BUN), Phosphorus, Calcium, Chloride, Sodium, Potassium, Bicarbonate, Glucose, CK, and CRP and ß2-microglobulin for multiple myeloma only. Fractionation of bilirubin (direct/indirect bilirubin or conjugated/unconjugated) must be performed in case of an elevation of total bilirubin.

Sponsor: Taiho Oncology, Inc. Protocol: TPU-TAS-120-101

Version: 3.3, Phase 1 Dose Escalation Only

# Statistical Analysis Plan

Urine sample for qualitative analysis are only collected at baseline (within 7 days prior to study medication administration on Day 1 of Cycle 1), within 24 hours prior to study medication administration on Day 1 beginning with Cycle 2, the end of treatment visit and 30-day safety follow-up visit. The following parameters will be measured: protein, glucose, and urine density.

The website http://www.globalrph.com/conv\_si.htm provides conversion factors between SI units and Conversion units.

The CTCAE grades of Hemoglobin, Platelet, INR, APTT, White blood cell (WBC) count with differential, Neutrophils, Lymphocytes, Fibrinogen, ALT (SGPT), AST (SGOT), Alkaline phosphatase, Bilirubin, Albumin, Creatinine, Calcium, Sodium, Potassium, and Glucose will be determined using computer algorithm only based on the numerical component of CTCAE v4.03 grading scale. For the parameters with uni-directional criteria, the CTCAE grade will be derived from 0 to 4. For the parameters with bidirectional criteria, the CTCAE grade will be derived from both low and high direction. Grade 0 is defined for a non-missing value which doesn't meet any criteria and within the normal range.

The worst severity grade during the treatment and 30 days follow-up will also be summarized descriptively. For the parameter with bi-directional criteria, both highest and lowest grade will be summarized. The worst grade in cycle 1 also will also be summarized in same way.

The shift in CTCAE grades from baseline to the worst grade in Cycle 1, and Entire Study for bi-directional parameters and unidirectional parameters will be presented. For all lab tests, a shift table in normal range from baseline to the worst grade in Cycle 1, and Entire Study will also be presented.

All collected laboratory hematology, coagulation, serum chemistry and urinalysis results will be listed. The normal laboratory ranges provided by laboratory will be also listed.

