## Statistical Analysis Plan

- c) ≥ Grade 3 diarrhea lasting > 48 hours and unresponsive to antidiarrheal medication
- d) Grade 4 neutropenia lasting > 7 days
- e) Febrile neutropenia (absolute neutrophil count [ANC] < 1 000/mm3 with a single body temperature of > 38.3°C [101°F] or a sustained temperature of 8°C [100.4°F] for more than 1 hour).
- f) Grade 4 thrombocytopenia or Grade 3 thrombocytopenia associated with bleeding and requiring blood transfusion
- g) Corneal disorder worsening by 1 grade or more
- h) Hyperphosphatemia: any increase of phosphorus 9mg/dL or an increase of phosphorus  $\geq$  7mg/dL lasting for 7 days or more despite phosphate -lowering therapy for 7 days as outlined in Appendix C or according to institutional guidelines.
- i) Increase of creatinine (> 1.5 × upper limit of normal [ULN]) lasting for 7 days or more associated with serum phosphorus > 5.5 mg/dL despite phosphate-lowering therapy for 7 days and/or calcium × phosphorus > 55 mg/dL despite phosphatelowering therapy for 7 days.
- j) Grade 2 hypercalcemia for > 7 days or Grade 3 hypercalcemia
- k) Ectopic de novo calcification in soft tissues, as determined by the investigator
- Any > Grade 2 drug-related toxicity that prevents completion of Cycle 1 (> 80% administration of intended dose of TAS-120)
- m) Inability to start Cycle 2 within 2 weeks of schedule due to a > Grade 2 drugrelated toxicity.

The MTD of TAS-120 is defined as the highest dose level at which less than 33% of the patients experience a DLT during Cycle 1. At least 6 evaluable patients will be enrolled to establish the MTD.

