## Statistical Analysis Plan

## 7. GENERAL ASPECTS FOR STATISTICAL ANALYSIS

#### 7.1. GENERAL METHODS

All relevant data will be presented in patient data listings.

All categorical (binary and ordinal) data will be summarized using frequency counts and percentages of patients. Percentage will be calculated using the corresponding treatment group in the study population as the denominator. The continuous variables will be summarized using number of non-missing observation (n), mean, standard deviation (SD), median, minimum and maximum unless otherwise specified. For example, the numbers of events and censorings will be reported for time-to-event analysis. All estimations will include a point estimate and the corresponding 95% confidence interval.

Summary tables will be presented by dosing schedule (i.e., QOD and QD), dose level and overall. Data listings will be ordered by assigned dosing schedule, dose level and patient ID. The dose levels presented in tables and listings for Phase 1 Dose Escalation are:

8 mg QOD, 16 mg QOD, 24 mg QOD, 36 mg QOD, 56 mg QOD, 80 mg QOD, 120 mg QOD, 160 mg QOD, 200 mg QOD, 240 mg QOD;

4 mg QD, 8 mg QD, 16 mg QD, 20 mg QD, 24 mg QD, 36 mg QD, 56 mg QD, 80 mg QD, 120 mg QD, 160 mg QD, 200 mg QD, and 240 mg QD if applicable.

For concomitant medications and adverse events, the cycles are determined based on their start/onset dates. For other collected data, the cycles are determined based on their visit dates.

When there are multiple laboratory records for a scheduled visit, the one closest to the target date (relative to the Day 1 in that cycle) will be used for analysis. If there are two or more records with the same time period to the target date, the later one will be used for analysis. However, the baseline for laboratory test is the defined as the latest laboratory result prior to the first dose of study medication.

All the analyses of safety, efficacy and pharmacodynamics data for this study will be performed using SAS® statistical software package. Version 9.3 or a later version.

Sponsor: Taiho Oncology, Inc. Protocol: TPU-TAS-120-101

Version: 3.3, Phase 1 Dose Escalation Only

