#### 17.2.5.2. Table Conventions

- Units will be included where available
- If the categories of a parameter are ordered, then all categories between the maximum and minimum category should be presented in the table, even if n=0 for all dose levels in a given category that is between the minimum and maximum level for that parameter. For example, the frequency distribution for symptom severity would appear as:

Severity	N
Rating	
severe	0
moderate	8
mild	3

Where percentages are presented in these tables, zero percentages will not be presented and so any counts of 0 will be presented as 0 and not as 0 (0%).

- If the categories are not ordered (e.g., Medical History, Reasons for Discontinuation from the Study, etc.), then only those categories for which there is at least 1 subject represented in 1 or more dose levels should be included.
- An Unknown or Missing category may be added to any parameter for which information is not available for 1 or more patients.
- Unless otherwise specified, the estimated mean and median for a set of values should be printed out to 1 more significant digit than the original values, and standard deviations should be printed out to 2 more significant digits than the original values. The minimum and maximum should report the same significant digits as the original values. For example, for systolic blood pressure:

N	XX
Mean	XXX.X
Std Dev	X.XX
Median	XXX.X
Minimum	XXX

CC

Sponsor: Taiho Oncology, Inc. Protocol: TPU-TAS-120-101

Version: 3.3, Phase 1 Dose Escalation Only

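### The Dose Escalation SAP's Grade 0 rule leaves a laboratory value that is abnormal on the harmless side ungraded, so the patient may be unclassified in that toxicity's shift table

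*SAP*

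**What the plan says.** Section 10.4 (Laboratory Evaluations) of the Dose Escalation SAP grades a list of laboratory tests, platelets and calcium among them, by algorithm from the numerical part of CTCAE v4.03. It sets three rules:

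- One-directional tests: "For the parameters with uni-directional criteria, the CTCAE grade will be derived from 0 to 4".
- Two-directional tests: "For the parameters with bidirectional criteria, the CTCAE grade will be derived from both low and high direction".
- Grade 0: "Grade 0 is defined for a non-missing value which doesn't meet any criteria and within the normal range".

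The grades feed a summary of worst grade and a shift table, described as "The shift in CTCAE grades from baseline to the worst grade in Cycle 1, and Entire Study for bi-directional parameters and unidirectional parameters". A second output sits beside it: "For all lab tests, a shift table in normal range from baseline to the worst grade in Cycle 1", with the same table for the entire study. All collected results are listed, along with the laboratories' normal ranges.

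The SAP has no rule for a non-missing value that receives no grade. The nearest provisions are general. Section 17.2.5.2 allows that "An Unknown or Missing category may be added to any parameter for which information is not available for 1 or more patients". On denominators, Section 7.1 says "Percentage will be calculated using the corresponding treatment group in the study population as the denominator", while Section 17.2.5.2 uses the patients in the treatment group who have an observation.

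**The concern.** A toxicity grade answers one question: how far has this value moved in the harmful direction? A value that has not moved that way at all has no toxicity and should be Grade 0. The second condition in the SAP's rule asks something else, namely whether the value is normal. A platelet count above the upper limit is not normal, but it is not thrombocytopenia either. Because the rule demands both conditions, such a value has no grade to take.

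The grading is done by program, so the sentence is in effect a specification. Section 18 calls for independent programming with electronic comparison. That check would not find the problem if both programmers followed the same sentence. At stake is whether the CTCAE shift table can classify every patient who has valid data.

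**Working it through.** The plan gives no figure on this point to reproduce. The check applies the rule literally to one one-directional test and follows it into the shift table.

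**Inputs**

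- Grade cut-offs for platelets, from protocol Section 8.1.3.1.2, Table 8 (x10^9/L): Grade 1 below LLN down to 75; Grade 2 below 75 down to 50; Grade 3 below 50 down to 25; Grade 4 below 25. All run downward from LLN.
- LLN = 150 and ULN = 400. These are assumed for illustration; the documents give no limits.
- Literal rule: Grade 1 to 4 if a cut-off is met; Grade 0 if none is met and LLN <= value <= ULN; otherwise no grade.
- Corrected rule: Grade 1 to 4 if a cut-off is met; otherwise Grade 0.

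**Step 1: single values**

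| Value | Literal rule | Corrected rule |
|---|---|---|
| 20 | 4 | 4 |
| 60 | 2 | 2 |
| 120 | 1 | 1 |
| 250 | 0 | 0 |
| 450 | no grade | 0 |

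Only the value above normal differs.

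**Step 2: shift from baseline to worst post-baseline grade**

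| Patient | Baseline | Post-baseline | Literal rule | Corrected rule |
|---|---|---|---|---|
| a | 450 | 300, 60 | none to 2 | 0 to 2 |
| b | 250 | 450, 260 | 0 to 0 | 0 to 0 |
| c | 250 | 450, 460 | 0 to none | 0 to 0 |
| d | 250 | 450, 60 | 0 to 2 | 0 to 2 |

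Patient a has no baseline cell, so a fall to Grade 2 has no place in the grade shift table. Patient c has no post-baseline cell. Patients b and d each have a high post-baseline value and are still classified, because the table takes the worst grade in the window. The gap therefore opens only when the baseline value, or every post-baseline value in the window, lies on the harmless side.

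**Step 3: two-directional tests**

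Two readings of Section 10.4 are possible. If each direction has its own 0-to-4 scale, a low calcium has no grade for hypercalcemia, and Steps 1 and 2 apply. If the grades form one signed scale (low grades, zero, high grades), a graded low calcium has its place on that scale, and a later rise appears as a low-to-high shift with no cell lost. The section plans to summarise a lowest as well as a highest grade for these tests, which fits the second reading. The text does not decide between the two.

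**The case against.** The strongest reply is that little is lost. It is largely right about the consequences:

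- **Dropping out of the table.** A reader might infer that affected patients disappear. No section says so. Section 17.2.5.2 permits an unknown or missing category, so patient a could appear as missing to Grade 2. The Section 7.1 denominator would keep the patient in, although Section 17.2.5.2 words its denominator differently. Exclusion is one possible outcome, not a stated one. A missing category would, however, label a known result as unknown.
- **Hidden toxicity.** A reader might infer that a later Grade 2 or 3 event goes unreported. It does not: the worst-grade summary needs no baseline grade, so the event appears there. Patient c has no toxicity to hide and is absent only from the Grade 0 row.
- **Calcium and DLTs.** Hypercalcemia is a DLT criterion in Section 4.1.1 ("Grade 2 hypercalcemia for > 7 days or Grade 3 hypercalcemia"), and entry allows low baseline calcium. It is tempting to conclude that the gap could mask a DLT. Nothing in the SAP sends the shift table into DLT or MTD decisions; DLTs have their own criteria, table and listing. The calcium example also depends on the separate-scale reading.
- **Patient counts.** One could multiply an assumed share by the 86 Dose Escalation patients and call the product patients lost. The share is not in the documents, and the last step assumes exclusion. No such count is supported.
- **Other outputs.** The normal-range shift table and the listings show the value whatever its grade.

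The reply does not rescue the sentence for one-directional tests. There the literal rule gives a valid result no grade, and no other section supplies one.

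**Conclusion.** The Grade 0 definition is wrong as written, and the effect is minor. For one-directional tests, a non-missing value outside normal on the harmless side gets no CTCAE grade. For two-directional tests the same holds only if each direction is graded separately, which Section 10.4 leaves open. The possible consequence is an unclassified baseline or post-baseline cell in one toxicity's grade shift table, under the condition found in Step 2. The number of patients cannot be sized from the documents. The conclusion rests on reading the sentence literally, which is reasonable for a rule to be programmed. It does not depend on the platelet limits assumed above, because any count above the upper limit behaves the same way.

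**What to change.** Replace the Grade 0 sentence in Section 10.4 of the Dose Escalation SAP with: *Grade 0 is assigned, separately for each direction graded, to any non-missing value that meets no CTCAE criterion in that direction.* This drops the normal-range condition and also settles how two-directional tests are scaled. Keep the planned normal-range shift table, which is the right place to show values that are abnormal but not toxic.

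The cost is one sentence and, if the program follows the current text, one line of code. If the program already works the corrected way, the edit only brings the SAP into line with it.

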### 10.5. VITAL SIGNS AND BODY WEIGHT

Vital signs (blood pressure, heart rate, body temperature, and respiration rate) and body weight are collected at baseline (within 7 days prior to study medication administration on Day 1 of Cycle 1), within 24 hours prior to study drug administration on Day 1 beginning with Cycle 2, the end of treatment visit and 30-day safety follow-up visit.

The observed values of vital sign and weight and their changes from baseline at these scheduled visits will be summarized descriptively by cohort and overall. When the

Sponsor: Taiho Oncology, Inc. Protocol: TPU-TAS-120-101

Research\*

Version: 3.3, Phase 1 Dose Escalation Only

## Statistical Analysis Plan

multiple results recorded at the same visit, the last valid result will be used for the summary. All values for vital sign and weight collected on eCRFs will be listed.

#### 10.6. ECG

The 12-lead resting electrocardiogram (ECG) are performed at screening (within 28 days prior to the study medication administration on Day 1 of Cycle 1), 2 hours after the dose on Day 1 of Cycle 1 and the last Wednesday of Cycle 1 (QOD arm) or 2 hours after study medication administration on Day 1 and Day 21 of Cycle 1 (QD arm) for patients enrolled in Phase 1 Dose Escalation, and the end of treatment visit and 30-day follow-up visit. For UK Protocol version, the 12-lead resting ECG is also performed at Day  $1 \pm 3$  days beginning with Cycle 3 (Phase 1 Dose Escalation).

A summary table reported the counts and percentage of Normal and Abnormal (CS, NCS) ECG will be presented for safety population and UK safety subgroup.

For QT Interval, and its Fridericia's correction, the absolute QT/QTc interval prolongation are defined in three different ways as: (1) QT (QTc) interval>450 ms; (2) QT (QTc) interval>480 ms; (3) QT (QTc) interval>500 ms. The change from baseline in QT (QTc) interval are defined in two different categories as: (1) QT(QTc) interval increases from baseline >30 ms; (2) QT(QTc) interval increases from baseline >60 ms. The number and percentage of patients meeting the above different categories will be summarized by dose level and overall for safety population and UK safety subgroup. A graph for QT interval and its Fridericia's correction may also be presented.

